7 STATISTICAL AND ANALYTICAL ISSUES

7.1 General Rules

All statistical computations will be performed and data summaries will be created using SAS 9.4 or higher. If additional statistical packages are required, these will be discussed in the study report. For summaries of study data, categorical measures will be summarized in tables listing the frequency and the percentage of subjects in each study arm; continuous data will be summarized by presenting mean, standard deviation, and where appropriate, minimum, and maximum values. Non-normal continuous data will be summarized by only presenting median and interquartile range (25th and 7th percentile).

7.2 Adjustments for Covariates

Indicator variables for the study stratification factors of site and age group ($\geq 65, < 65$) will be included as covariates in most efficacy analyses performed for this study (details in section 9). The baseline value of the outcome variable will also be a covariate in models of change from baseline.

Additionally, demographic and baseline characteristics will be compared between study arms using a t-test for continuous measures, Mantel-Haenszel mean score test using standardized midrank scores for ordinal measures, and Cochran Mantel-Haenszel chi-square tests for general association for categorical measures. If these analyses suggest that a substantial difference exists among arms for an important characteristic, supportive exploratory analyses of the primary efficacy outcome adjusting for the characteristic may be explored.

7.3 Handling of Dropouts and Missing Data

The repeated measures analysis for the primary outcome for the MITT population (see Section 9.3) assumes missing data due to a missed visit or early study discontinuation is missing at random. The impact of missing data on the primary efficacy MITT analysis results will be explored through multiple imputation sensitivity analyses using control-based imputation if more than 10% of participants in the mITT population are missing their 6-month UDI score and a treatment group difference is identified, in order to assess the robustness of the primary results to missing data. (See Section 9.3). Sensitivity analyses are not planned for secondary or other outcomes.

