6.2 Statistical Analysis Plan

6.2.1 Analysis Populations and Management of Study Discontinuations Prior to Receiving Treatment

It is possible that some women in both groups may cancel their surgical procedure due to personal or other reasons. Consistent with analyses for prior PFDN protocols (SUPeR, ASPIRe, ROSETTA), non-treated patients will be removed from evaluation of efficacy in a modified intent-to-treat population.

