6.2.2 Primary Aim

Primary Outcome

The mean change from baseline in UDI total score will be compared between groups at 6 months at the $p<0.05$ statistical significance level using a mixed effects analysis of covariance model for repeated measures (MMRM) with adjustment for baseline UDI score, and randomization stratification factors site and age group. The model will include fixed effect categorical factors for treatment group, visit (3 and 6 months), and treatment \times visit interaction with a heterogeneous Toeplitz covariance pattern for the within-subject repeated measures. Estimates, p-values and 95% confidence intervals will be presented for treatment group comparisons at 6 months (primary) and 3 months (secondary).

This model assumes missing data due to a missed visit or early study discontinuation is missing at random. If more than 10% of participants are missing their 6-month score, then a sensitivity analysis will be performed using multiple imputation under a variety of missing data patterns to be specified in the statistical analysis plan in order to assess the robustness of the primary results to missing data. .

We will report whether change in total UDI score from baseline to 6 months is statistically significantly different between groups. If the difference is statistically significant, the potential clinical significance of the difference will be discussed. We recognize that our sample size may allow us to find a difference between groups that is statistically significant yet smaller than published MID for total UDI score for women with MUI. However, published MIDs were calculated based on populations that may be somewhat different from the one targeted for enrollment in MUSA, and an exploratory aim of MUSA is to explore whether the MID in this population differs from previously published values.

Secondary Outcomes

There are two secondary outcomes for the primary aim. The mean change from baseline in UDI-stress and UDI-irritative subscores will be compared between groups at 6 months. Each of these outcomes will be evaluated using an alpha level of 0.05, with no adjustment for multiple comparisons. The statistical analysis of the two secondary outcomes will be identical to the analysis described above for the UDI total score.

6.2.3 *Exploratory Aims*

All statistical evaluations of the exploratory aims are for descriptive purposes and p-values resulting from these analyses will not be evaluated for statistical significance.

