5 ANALYSIS POPULATIONS

5.1 Modified Intention-to-Treat (mITT) Population

It is possible that some women in both groups may cancel their surgical procedure due to personal or other reasons. It is also possible that a treated participant might discontinue from the study after treatment while providing no efficacy data to be included in the analysis. The mITT population is defined as all randomized subjects, regardless of their final study status, that received any study treatment, and have some post-baseline efficacy data.

Unless otherwise specified, the mITT population will be used to analyze all efficacy outcomes. Subjects will be summarized according to the arm to which they were randomized, irrespective of the received treatment.

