Sensitivity analysis: This model assumes missing data due to a missed visit or early study discontinuation is missing at random (MAR). If more than 10% of participants are missing their 6-month score and a statistical difference is seen between groups at 5 months, then a sensitivity analysis in order to assess the robustness of the primary results to missing data will be performed using multiple imputation under a not -missing-at-random (NMAR) as follows: missing data from discontinuations in the arm found to be superior will be imputed based on data from the less superior arm ("control-based imputation"). (Ratitich et al 2013, 2,14). This sensitivity analysis essentially takes the conservative assumption that missing data after discontinuation in the superior arm have outcome values as if they were in the non-superior arm.

A supportive per-protocol analysis of the primary outcome will be based on the per-protocol population with data excluded (set value to missing) for any data points at 3 or 6 months that are collected after a cross-over treatment or additional therapy. Since crossing over and additional treatments were allowed after 6 months, data points after 6 months are not planned to be excluded in any sensitivity analyses.

Sensitivity of the per-protocol analysis: the data set to missing due to off-protocol treatments is assumed by the model to be missing at random. However, it is possible that if these measures were assessed without additional therapy, they might have reflected poor outcomes. To assess the impact of the results from the missing data, we will conduct a tipping point multiple imputation analysis, in which the missing values are increased (worsened) by a fixed value, in successive intervals across successive analyses until a point at which statistical interpretation of the p-value at 6 months between treatment groups is changed. (Ratitich et al 2013, 2,14).

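### The 10% missing-data trigger is counted on a narrowed mITT set, so treated women lost before any assessment never count towards it

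*SAP*

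**What the plan says.** **Protocol.** Section 6.2.1 defines the efficacy population by one exclusion: "non-treated patients will be removed from evaluation of efficacy in a modified intent-to-treat population". Section 6.2.2 then gives the missing-data rule: "If more than 10% of participants are missing their 6-month score, then a sensitivity analysis will be performed using multiple imputation". It leaves the imputation patterns to the SAP but sets the 10% count itself.

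**SAP.** Section 5.1 notes that "a treated participant might discontinue from the study after treatment while providing no efficacy data to be included in the analysis", and so limits mITT to randomised women "that received any study treatment, and have some post-baseline efficacy data". Section 7.3 attaches the trigger to that set: "if more than 10% of participants in the mITT population are missing their 6-month UDI score", with the further condition that a group difference is found. Section 9.3 repeats the rule without naming a population ("If more than 10% of participants are missing their 6-month score") and specifies the method: missing values after discontinuation in the better arm are imputed from the other arm's data. Section 13, which is reserved for departures from the protocol's analysis, lists only the covariance structure.

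**The concern.** Protocol 6.2.2 and SAP 9.3 both present the sensitivity analysis as a test of the missing-at-random assumption for missed visits and early discontinuation. A treated woman who leaves before giving any efficacy data is the clearest case of early discontinuation. Under SAP 5.1 she is not in mITT, so under SAP 7.3 she leaves both the numerator and the denominator of the trigger. If the imputation is run, it is run without her.

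No other planned analysis picks her up. The tipping-point analysis in SAP 7.4 and 9.3 works on the per-protocol set, which SAP 5.2 defines as a subset of mITT. Participants and surgeons are not masked, so loss soon after treatment could differ by arm. The documents give no data on whether it does. At stake is whether the robustness check is run when it should be, and on whom.

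**Working it through.** **Inputs.** Randomised: 146 (SAP 6). Threshold: more than 10% (Protocol 6.2.2, SAP 7.3 and 9.3). Planned 6-month loss: 5% (SAP 6). ESTEEM sling-arm 6-month discontinuation: 16/235 = 6.8% (Protocol Table 10). The number of treated women without post-baseline data is not given, so it is varied below.

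**The plan's own figure.** With a difference of 26, SD 46.5 and two-sided alpha 0.05, the noncentral t gives 89.9% power at 68 per arm and 90.3% at 69. So 69 evaluable per arm is right. Then 69/0.95 = 72.6, rounded up to 73 per arm, or 146 in total. The stated sample size reproduces.

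**The two counts.** Let T be the number of randomised and treated women, k those of them with no post-baseline efficacy data, and m the women inside the SAP's mITT who lack the 6-month UDI-total.

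- Protocol base (treated women): condition met if (m + k)/T > 0.10.
- SAP base (treated, with some data): condition met if m/(T − k) > 0.10.

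The rules disagree when m ≤ 0.10 × (T − k) while m + k > 0.10 × T.

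**All 146 treated (T = 146).** The protocol base is met at 15 missing (15/146 = 10.3%; 14/146 = 9.6% is not enough).

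| k (assumed) | Largest m that does not trigger | SAP rate | Rate among all treated |
|---|---|---|---|
| 0 | 14 | 14/146 = 9.6% | 14/146 = 9.6% |
| 1 | 14 | 14/145 = 9.7% | 15/146 = 10.3% |
| 2 | 14 | 14/144 = 9.7% | 16/146 = 11.0% |
| 4 | 14 | 14/142 = 9.9% | 18/146 = 12.3% |

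**Fewer treated.** Suppose 8 women are never treated (an assumption), so T = 138. With k = 0, both bases read 13/138 = 9.4% at m = 13, so untreated women alone create no gap. With k = 1, the SAP rate is 13/137 = 9.5% and the rate among treated women is 14/138 = 10.1%. One woman is enough unless T is an exact multiple of 10, when it takes two: for T = 140 and k = 2, 13/138 = 9.4% against 15/140 = 10.7%.

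**How often 10% would be passed at all.** With independent losses among 146 women, the binomial chance of 15 or more missing is 0.7% at the planned 5% (expected 0.05 × 146 = 7.3 women) and 7.3% at ESTEEM's 6.8% (expected 9.9 women).

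**The case against.** A reader might infer three stronger points, which the documents do not support.

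1. *The SAP has two conflicting denominators.* SAP 9.3 names no population, but SAP 5.1 and 9.1 make mITT the default for efficacy and SAP 7.3 sends the reader to 9.3. Its participants are naturally read as mITT. This is loose wording, not a contradiction.
2. *All non-mITT women are hidden by the SAP.* Protocol 6.2.1 already removes untreated women before 6.2.2 states the 10% rule. The SAP adds only treated women with no efficacy data. To be dropped, a woman must have none at 3, 6, 9 or 12 months; one with a 3-month value alone stays in and counts as missing at 6 months. Gaps between randomised and treated numbers in earlier trials say nothing about this group.
3. *Below the trigger no sensitivity analysis is run.* The per-protocol analysis of the primary outcome and its tipping-point imputation have no 10% condition. They address values removed after off-protocol treatment and do not include these women, but they are run regardless.

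It is also fair to say that counting missingness in the set being analysed is coherent, that such women add nothing to the repeated-measures model, and that the CONSORT diagram (SAP 8.1) and masked data review (SAP 7.6) will show early losses. All of this stands. But displaying a loss is not testing the result against it, and the narrowed base is still an undeclared departure from the protocol.

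**Conclusion.** The point holds in a limited form. The SAP narrows the protocol's mITT by requiring post-baseline data, counts the trigger on the narrowed set, and does not declare the change. Treated women lost before any assessment are therefore outside both the trigger and the control-based imputation. If all 146 are treated, one such woman lets missingness reach 10.3%, and four let it reach 12.3%, without meeting the condition.

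The practical effect is probably small. The number of such women is unknown, the values of k are assumptions, and at the planned 5% loss the threshold is passed on either base in under 1% of trials. The primary estimate does not change; only the decision to test it, and the women in that test, do. This is a cheap improvement, not a flaw that threatens the trial. The further requirement of a group difference is a separate matter and is left aside here.

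**What to change.** - In SAP 7.3 and 9.3, state one missingness condition: more than 10% of all randomised and treated women (the protocol's mITT base) lack a 6-month UDI-total.
- In the control-based imputation, include treated women with no post-baseline data, using baseline UDI, site, age group and arm.
- In SAP 13, list the added post-baseline-data requirement and its reason.

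Leave the group-difference condition as it is under this point. The cost is a few lines of SAP text, a slightly wider set for the imputation than for the primary model, and a slightly higher chance of having to run an analysis that is already specified.

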7.4 Handling of Cross-over and off-study treatment

It is a protocol deviation for participants to receive any other UI treatments during the first 6 months after treatment. After 6 months, participants may cross-over to receive their non-randomized treatment and may also receive additional off-study UI treatments.

For all primary mITT analyses, data for participants who cross-over and receive the other study treatment or receive an off-study treatment during the first 6 months will be included in all analyses in an intent-to-treat fashion.

The mITT analysis is conservative as it may minimize differences between groups or bias results to make a treatment appear more efficacious due to inclusion of data after a participant has received the other study treatment or additional treatments. Therefore, a supportive per-protocol analysis of the primary and 3 secondary outcomes will be based on the per-protocol population with data excluded (value set to missing) for any data points at 3 or 6 months that are collected after a cross-over treatment or additional therapy. Since crossing over and additional treatments were allowed after 6 months, data points after 6 months will not be excluded. See Section 9.3.

The per-protocol analysis is expected to remove bias in outcome caused by the off-protocol additional therapies, in order to provide a more accurate estimate of the true difference in UDI 6 months after the randomized treatment with no further interventions.

The repeated measures analysis assumes that the values set to missing after cross-over treatment are missing at random. However, since additional treatment was sought, it's possible that the outcome scores with no extra treatment received, had they been available, would reflect poorer outcome scores than other recorded data, and thus not be missing at random. Therefore, a multiple imputation tipping point sensitivity analysis of the per-protocol analysis will be conducted. Tipping point analysis will consist of a set of multiple imputation analyses in which the imputed UDI change from baseline scores are increased (made worse) by successively fixed amounts, in order to identify at what amount would have a change in the interpretation of the per-protocol analysis. See Section 9.3

7.5 Interim Analyses and Data Monitoring

Safety outcomes will be assessed at each DSMB meeting. This will include the need for sling revision due to worsening OAB symptom.

No formal interim analyses of efficacy outcomes will be performed. At each meeting, the DSMB will be presented with information about enrollment, participant adverse events, and outcome

data attainment (for example, the percent of expected clinic visits that have been completed) to allow them to determine that the study is making reasonable progress. Interim efficacy data can be reviewed by the DSMB upon their request.

7.6 Masked Data Review

A masked data review of the primary and secondary outcomes for this study will be performed by the protocol team. This review will occur prior to data lock analyses. This will include evaluation of missing data, descriptive statistics (e.g. means, standard deviations, percentiles for continuous variables and counts and percentages of categorical variables) of key efficacy and safety outcomes, protocol violations and model predictor variables. In the masked review, any summaries will be aggregated over both treatment groups.

7.7 Multicenter Studies

For this multicenter study, randomization of study participants was stratified within center and by age group ($\geq 65, < 65$). Consequently, for all model-based primary and secondary analyses, center and age group will be included as fixed effects in the models. There were 8 enrolling sites, each with at least 10 treated participants, so sites will not be pooled.

7.8 Multiple Comparisons and Multiplicity

The primary hypothesis will be tested at a nominal two-sided type I error of 0.05. The three secondary outcomes will also be tested at a nominal two-sided type 1 error of 0.05, with no adjustment for multiple comparisons, and thus p-values are descriptive. All p-values for any baseline and demographic characteristics, exploratory outcomes, and safety parameters will also be for descriptive purposes only.

7.9 Examination of Subgroups

We will evaluate the primary outcome for one pre-planned subgroup of interest, which is the type of mixed urinary incontinence based on the baseline UDI: stress-predominant, urgency-predominant, or balanced.

7.10 Assessment Windows

Baseline assessments were to be completed no longer than 3 months prior to intervention with assessments repeated if participant treatment is delayed for over 3 months. All other visits were completed at 2 weeks with $a \pm 1$ week window around the visit and 3-month intervals (3, 6, 9, 12 months) with $a \pm 1$ month window around the visit. Coordinators attempted to complete all follow-up visits, even if they couldn't be completed within window. For all analyses, all available data will be used regardless of if the assessment was completed within window or not.

8 STUDY SUBJECT CHARACTERIZATION

8.1 Subject Disposition

Disposition of study participants will be described using a standard Consort diagram, including the number of subjects screened, consented, randomized, treated, receiving protocol specified botox at 3-6 months, and completing or discontinuing from the treatment period prior to 6 months and from the 6-month follow-up period. Reasons for study withdrawal will be presented.

8.2 **Protocol Deviations**

Protocol deviations are identified via automated checks of the clinical database and reported by site study coordinators in the study data management system. For DSMB reports, protocol deviations will be listed by site with information such as type of deviation, time of occurrence, and reason, and incidence rate of protocol deviations will be summarized overall and for each

protocol deviation category. Incidence rate of protocol deviations will be calculated as: number of deviations divided by the number of subjects at the site.

Key protocol deviations are violations of inclusion/exclusion criteria, receipt of any off-protocol treatments for UI prior to the 6 month assessment, including switching arms, re-treatment of botox before 3 months, and any non-study UI treatment.

8.3 Demographic and Baseline Characteristics

Demographic and baseline clinical characteristics for the study participants will be summarized by study arm using the general analysis rules describe above. Variables of interest include age (years), parity, gravidity, race and ethnicity, BMI, education level (classified as binary variable as having some education greater than high school), smoking status (current yes or no), menopausal status, and estrogen use. Also included is time from baseline to treatment and percent of participants with > 91 days to treatment.

Baseline levels of all OAB and QOL measures will be presented on efficacy tables.

9 EFFICACY ANALYSES

9.1 Overview of Efficacy Analyses Methods

All efficacy analyses will be performed on the mITT population unless otherwise specified. All primary, secondary and exploratory efficacy variables were collected longitudinally across this study. Consequently, all efficacy analyses will be conducted using appropriate models for these correlated data collected across time. Specifically, continuous outcome variables will be analyzed using linear mixed models and binary outcome variables will be analyzed using generalized linear mixed models. Models will include terms for treatment and for the stratification variables included in the study design (site and age group (≥ 65 , < 65)). Additional details are provided in the specific sections below (See section 9.3).

9.2 Variable Definitions

Primary and secondary efficacy variables as well as exploratory and safety outcomes are described in the table below.

Note that for any patient who had a repeat baseline, their repeat measures will be used in the definition of baseline (their updated baseline scores were entered into the repeat baseline CRF by the sites).

Variable	Туре	Definition
Primary Outcomes		
type of urinary incontinence	Categorical stress-predominant urgency-predominant balanced	 The definition of the type of urinary incontinence will be based on 2 questions of the Urogenital Distress Inventory, 1. "Do you experience urine leakage associated with a feeling of urgency?" 2. "Do you experience urine leakage related to physical activity, coughing, or sneezing?" Based on our inclusion criteria, patients must report at least "moderate" bother on both questions. If the subject reports greater bother on the stress question, she will be classified as stress-predominant MUI. If the subject reports greater bother on the urgency question, she will be classified as urgency-predominant MUI. If the subject reports equal bother on both questions, she will be classified as "balanced" MUI.
Change from baseline in UDI Total Score at 6 months (and at 3, 9, and 12 months) 6 months is primary,	Continuous	The Urogenital Distress Inventory-Total Score will be computed at baseline and 6 months (and 3, 9, and 12 months) using the standard scoring algorithm. Specifically, the instructions are to sum the Stress, Irritative, and Obstructive subscales of the UDI (see below). If any subscale scores are missing, then the score will be calculated as the sum of the non-missing scales. The outcome will then be computed as the difference in Total score at 6 months (and 3, 9, and 12 months) and the Total score at baseline. If data for an assessment time point are missing, the outcome variable will be coded as missing.

Variable	Туре	Definition
Secondary Outcomes		
Change from baseline in UDI Obstructive Score at 6 months (and at 3, 9 and 12 months)	Continuous	The Urogenital Distress Inventory-Obstructive Score will be computed as baseline and 6 months (and 3, 9, and 12 months) using the standard scoring algorithm. Specifically, the instructions are to average responses across questions E, J, K, L, M, N, O, P, Q, R, and S and their respective sub-questions (0=No or Yes and Not at all; 1=Yes and Slightly; 2=Yes and Moderately; 3=Yes and Greatly), and then multiply by 100/3. If any responses are missing, then the score will be calculated as the average of the non-missing responses. The outcome will be computed as the difference in score at 6 months (and 3, 9, and 12 months) and the score at baseline. If data for an assessment time point are missing, the outcome variable will be coded as missing.
Change from baseline in UDI Stress Score at 6 months (and at 3, 9 and 12 months)	Continuous	The Urogenital Distress Inventory-Stress Score will be computed at baseline and 6 months (and 3, 9, and 12 months) using the standard scoring algorithm. Specifically, the instructions are to average responses across questions D and F and their respective sub- questions (0=No or Yes and Not at all; 1=Yes and Slightly; 2=Yes and Moderately; 3=Yes and Greatly), and then multiply by 100/3. If any responses are missing, then the score will be calculated as the average of the non-missing responses. The outcome will then be computed as the difference in score at 6 months (and 3, 9, and 12 months) and the score at baseline. If data for an assessment time point are missing, the outcome variable will be coded as missing.
Change from baseline in UDI Irritative Score at 6 months (and at 3, 9 and 12 months)	Continuous	The Urogenital Distress Inventory-Irritative Score will be computed at baseline and 6 months (and 3, 9, and 12 months) using the standard scoring algorithm. Specifically, the instructions are to average responses across questions A, B, C, G, H, and I and their respective sub-questions (0=No or Yes and Not at all; 1=Yes and Slightly; 2=Yes and Moderately; 3=Yes and Greatly), and then multiply by 100/3. If any responses are missing, then the score will be calculated as the average of the non-missing responses. The outcome will then be computed as the difference in score at 6 months (and 3, 9, and 12 months) and the score at baseline. If data for an assessment time point are missing, the outcome variable will be coded as missing.

Variable	Туре	Definition
Exploratory Outcomes		
Normalization of Voiding Frequency at 6 (and at 3 and 12 months)	Dichotomous (Yes/No)	The total number of daytime and nighttime voids will be taken from the bladder diary and summed and then divided by the number of diary days (<=3) to get a voiding frequency. The indicator for normalization at 6 months (and 3 and 12 months) will be defined for each subject as follows: If > 8 voids/24 hours at baseline: If > 8 voids/24 hours at time x: No If \leq 8 voids/24 hours at time x: Yes If \leq 8 voids/24 hours at baseline: Missing If data for the assessment time point are missing, the normalization indicator will be coded as missing. The variable is summarized as the percentage of participants with indicator equal to "Yes" among all non-missing indicators.
Improvement of 50% or more in Voiding Frequency at 6 months (and at 3 and 12 months)	Dichotomous (Yes/No)	The total number of daytime and nighttime voids will be taken from the bladder diary and summed and divided by the number of diary days (<=3) to get a voiding frequency. If there has been at least a 50% reduction in the voiding frequency between baseline and the time point, the improvement indicator at 6 months (and 3 and 12 months) will be set to "Yes", otherwise it will be set to "No". If data for the assessment time point are missing, the improvement indicator will be coded as missing. The variable is summarized as the percentage of participants with indicator equal to "Yes" among all non-missing indicators.
Worsening of Voiding Frequency at 6 months (and at 3 and 12 months)	Dichotomous (Yes/No)	The total number of daytime and nighttime voids will be taken from the bladder diary and summed and divided by the number of diary days (<=3) to get a voiding frequency. If there has been an increase of any amount between baseline and the time point, the worsening indicator at 6 months (and 3 and 12 months) will be set to "Yes", otherwise it will be set to "No". If data for the assessment time point are missing, the improvement indicator will be coded as missing.

Variable	Туре	Definition
		The variable is summarized as the percentage of participants with indicator equal to "Yes" among all non-missing indicators.
Change from baseline in Urge Incontinence Episodes at 6 months (and at 3 and 12 months)	Continuous	The daily frequency of urge incontinence episodes will be taken from the bladder diary. The outcome will then be computed as the difference in daily frequency of urge incontinence episodes at 6 months (and 3 and 12 months) and the daily frequency of urge incontinence episodes at baseline. If data for the assessment time point are missing, the outcome variable will be coded as missing.
Change from baseline in Stress Incontinence Episodes at 6 months (and at 3 and 12 months)	Continuous	The daily frequency of stress incontinence episodes will be taken from the bladder diary. The outcome will then be computed as the difference in daily frequency of stress incontinence episodes at 6 months (and 3 and 12 months) and the daily frequency of stress incontinence episodes at baseline. If data for the assessment time point are missing, the outcome variable will be coded as missing.
Change from baseline in Mixed or Don't Know Incontinence Episodes at 6 months (and at 3 and 12 months)	Continuous	The daily frequency of mixed urge and stress incontinence episodes will be taken from the bladder diary. The outcome will then be computed as the difference in daily frequency of mixed incontinence (noted on diary as "both stress/urge") or "don't know" episodes at 6 months (and 3 and 12 months) and the daily frequency of mixed incontinence episodes at baseline. If data for the assessment time point are missing, the outcome variable will be coded as missing.
Change from baseline in Total Incontinence Episodes at 6 months (and at 3 and 12 months)	Continuous	The daily frequency of total incontinence episodes will be taken from the bladder diary. The outcome will then be computed as the difference in daily frequency of total incontinence episodes at 6 months (and 3 and 12 months) and the daily frequency of total incontinence episodes at baseline. If data for the assessment time point are missing, the outcome variable will be coded as missing.

Variable	Туре	Definition				
Change from baseline in Nocturnal voids at 6 months (and at 3 and 12 months)	Continuous	The daily frequency of total nighttime voids will be taken from the bladder diary. The outcome will then be computed as the difference in daily frequency of nighttime voids at 6 months (and 3 and 12 months) and the daily frequency of nighttime voids at baseline. If data for the assessment time point are missing, the outcome variable will be coded as missing.				
Change from baseline in Diurnal voids at 6 months (and at 3 and 12 months)	Continuous	The daily frequency of total daytime voids will be taken from the bladder diary. The outcome will then be computed as the difference in daily frequency of daytime voids at 6 months (and 3 and 12 months) and the daily frequency of daytime voids at baseline. If data for the assessment time point are missing, the outcome variable will be coded as missing.				
Change from Baseline OAB- q Symptom Severity Score at 3, 6, 9, 12 Months	Continuous	The OAB-q Symptom Severity Score will be computed at baseline and 6 months (and 3, 9, and 12 months) using the standard scoring algorithm. Specifically, instructions are to sum responses across questions 1 through 8 (1= Not at all, 2=A little bit, 3=Somewhat, 4=Quite a bit, 5=A great deal, 6=A very great deal), then subtract the minimum possible score (8) and divide by the range of possible score (48-8=40), then multiply by 100. If less than half of the responses are missing, then the score will be calculated by substituting the missing responses with the average of the non-missing responses, otherwise no score is calculated. The outcome will then be computed as the difference in score at 6 months (and 3, 9, and 12 months) and the score at baseline. If data for an assessment time point are missing, the outcome variable will be coded as missing.				
Change from Baseline OAB- q HRQL Coping Score at 3, 6, 9, 12 Months	Continuous	The OAB-q HRQL Coping Score will be computed at baseline and 6 months (and 3, 9, and 12 months) using the standard scoring algorithm. Specifically, instructions are to sum responses across questions 9, 11, 16, 21, 22, 26, 32, and 33 (1= None of the time, 2=A little bit of the time, 3=Some of the time, 4=A good bit of the time, 5=Most of the time, 6=All of the time), then subtract from the maximum possible score (48) and divide by the range of possible score (48-8=40), then multiply by 100. If less than half of the responses are missing, then the score will be calculated by substituting the missing responses with the average of the non-missing responses, otherwise no score is calculated. The outcome will then be computed as the difference in score at 6 months				

Variable	Туре	Definition			
		(and 3, 9, and 12 months) and the score at baseline. If data for an assessment time point are missing, the outcome variable will be coded as missing.			
Change from Baseline OAB- q HRQL Concern Score at 3, 6, 9, 12 Months	Continuous	The OAB-q HRQL Concern Score will be computed at baseline and 6 months (and 3, 9, and 12 months) using the standard scoring algorithm. Specifically, instructions are to sum responses across questions 12, 13, 14, 19, 23, 25, and 29 (1= None of the time, 2=A little bit of the time, 3=Some of the time, 4=A good bit of the time, 5=Most of the time, 6=All of the time), then subtract from the maximum possible score (35) and divide by the range of possible score (42-7=35), then multiply by 100. If less than half of the responses are missing, then the score will be calculated by substituting the missing responses with the average of the non-missing responses, otherwise no score is calculated. The outcome will then be computed as the difference in score at 6 months (and 3, 9, and 12 months) and the score at baseline. If data for an assessment time point are missing, the outcome variable will be coded as missing.			
Change from Baseline OAB- q HRQL Sleep Score at 3, 6, 9, 12 Months	Continuous	The OAB-q HRQL Sleep Score will be computed at baseline and 6 months (and 3, 9, and 12 months) using the standard scoring algorithm. Specifically, instructions are to sum responses across questions 10, 15, 17, 24, and 30 (1= None of the time, 2=A little bit of the time, 3=Some of the time, 4=A good bit of the time, 5=Most of the time, 6=All of the time), then subtract from the maximum possible score (30) and divide by the range of possible score (30-5=25), then multiply by 100. If less than half of the responses with the average of the non-missing responses, otherwise no score is calculated. The outcome will then be computed as the difference in score at 6 months (and 3, 9, and 12 months) and the score at baseline. If data for an assessment time point are missing, the outcome variable will be coded as missing.			
Change from Baseline OAB- q HRQL Social Score at 3, 6, 9, 12 Months	Continuous	The OAB-q HRQL Social Score will be computed at baseline and 6 months (and 3, 9, and 12 months) using the standard scoring algorithm. Specifically, instructions are to sum responses across questions 18, 20, 27, 28, and 31 (1= None of the time, 2=A little bit of the time, 3=Some of the time, 4=A good bit of the time, 5=Most of the time, 6=All of			

Variable	Type Definition				
		the time), then subtract from the maximum possible score (30) and divide by the range of possible score (30-5=25), then multiply by 100. If less than half of the responses are missing, then the score will be calculated by substituting the missing responses with the average of the non-missing responses, otherwise no score is calculated. The outcome will then be computed as the difference in score at 6 months (and 3, 9, and 12 months) and the score at baseline. If data for an assessment time point are missing, the outcome variable will be coded as missing.			
Change from Baseline OAB- q HRQL Total Score at 3, 6, 9, 12 Months		The OAB-q HRQL Total Score will be computed at baseline and 6 months (and 3, 9, and 12 months) using the standard scoring algorithm. Specifically, instructions are to sum the OAB-q HRQL Coping, Concern, Sleep, and Social prior to subtracting from the respective maximum possible scores, then subtract from the maximum possible sum score (150) and divide by the range of possible scores ((18+42+30+10=150)-(8+7+5+5=25)=125), then multiply by 100. The outcome will then be computed as the difference in score at 6 months (and 3, 9, and 12 months) and the score at baseline. If any of the listed subscales are missing, the Total score will also be set to missing. If data for an assessment time point are missing, the outcome variable will be coded as missing.			
OAB-SAT-q Satisfaction Score at 3, 6, 9, 12 Months	Continuous	 NOTE: The scoring manual for the OAB-SAT-q states that higher scores should correspond to better outcomes and details that final composite scores for each dimension should be obtained by subtracting raw scores from the highest possible score and dividing by range. However, based on the direction of score for individual responses, this derivation would result in lower scores corresponding with better outcomes. We have adjusted the scoring algorithm instead to be: 100*(raw score – lowest possible score)/score range. This calculation results in higher scores corresponding to better outcomes and an overall scale of 0-100. The OAB-SAT-q Satisfaction Score will be computed at 6 months (and 3, 9, and 12 months) using the standard scoring algorithm. Specifically, instructions are to sum responses across questions 1, 2, and 3 (1=Extremely Dissatisfied,, 6=Extremely Satisfied), then subtract the lowest possible score (3) from the raw score and divide by the range of possible scores (18-3=15), then multiply by 100. If less than half of the 			

Variable	Туре	Definition				
		responses are missing, then the score will be calculated by substituting the missing responses with the average of the non-missing responses, otherwise no score is calculated. If data for an assessment time point are missing, the outcome variable will be coded as missing.				
